Peak flow meter	X*	X	X#	X*		X	X#	X#	Note: only for subjects aged 4 to < 6 years * Prior to initiating series of DBPCFCs in non- asthmatic and prior to each DBPCFC in asthmatic subjects. *If clinically indicated per investigator's discretion.
Pulse oximetry	X ⁺	X	X* (updosing)	X ⁺		X			*To be performed in all subjects as a complement to spirometry prior to each DBPCFC in the series or updosing procedure *Not required at Week 38
DBPCFC	X*			X#		X^			To be overseen by a physician or qualified clinician designee. Study drug is not to be taken on the day of an Exit DBPCFC. *Screening DBPCFC: refer to Figure 2. *Exit DBPCFC: refer to Figure 4. ^ET DBPCFC: consult Study Medical Monitor

Note: Refer to Appendix 6	(Section 10.	6) for guid			sessments a	nd pr	rocedur	es duri	ng public health emergency.
		Treatment Period] !		Notes
Procedure	Screening*	Day1/BL	Week 2–38 [‡] (every 2 weeks)	Week 40#	ЕОТ	ЕТ	UNS&	FU^	*Screening will be done over multiple visits. †When a subject completes updosing, every other visit can occur over the telephone.
Visit window	≤ 12 weeks before Day 1	NA	±4 days	-2 days to +6 weeks	Up to +4 weeks from last Exit DBPCFC	NA	NA	±5 days	*Week 40 visit can be done over multiple visits over 6 weeks to accommodate multiple Exit DBPCFCs. This period may be extended to up to 8 weeks if a subject requires > 6 food challenges. *Unscheduled visit as clinically indicated. ^Follow-up visit will be 14 days post-EOT, only for subjects who will not continue to the OLE.
Dispense stool collection kit	X*		Week 38 only						Note: For microbiome analysis. *Subjects should collect the sample prior to dosing with study drug
FAQLQ	X*		Week 20	X*	X	X			*Administer prior to the first Screening and Exit DBPCFC.
IQoL	X*		Week 20	X*	X	X			*Administer prior to the first Screening and Exit DBPCFC.
ACT ⁺ or C-ACT ⁺	X*			X*	X	X			*Administered prior to the first Screening and Exit DBPCFC. *For subjects with asthma only.
FAQL-PB questionnaire	X*		Week 20	X*	X	X			*Administer prior to the first Screening and Exit DBPCFC.
TSQM-9			Week 20	X*	X	X			*Administer prior to the first Exit DBPCFC.
Training on DISP		X	Weeks 12, 24, and 38						
Blood draw for exploratory biomarkers		X	Week 20; Week 38			X			Note: To be used to evaluate additional biomarkers including, but not limited to, PBMC, microRNA, and DNA methylation (as outlined in Section 8.4).
Train subject on mApp		X							

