7.3. Subject Withdrawal from the Study

Subjects have the right to withdraw from the study at any time and for any reason without prejudice to their future medical care by the investigator or at the institution. Subjects may withdraw from the study for reasons including, but not limited to, the following:

- Death
- Withdrawal by subject/legally authorized representative
- Lost to follow-up
- Termination of study by Sponsor

The reason for subject withdrawal from the study will be recorded in the source documentation and on the appropriate eCRF.

If a subject is withdrawing from the study and has previously discontinued study drug, if possible, an Early Termination (ET) visit should be conducted, as shown in the SoA (Section 1.3). If the subject is simultaneously discontinuing study drug and withdrawing early from the study, the ET visit should be conducted. The subject should be encouraged to return for the follow-up visit. See the SoA for data to be collected at the time of study withdrawal and at follow-up and for any further evaluations that need to be completed.

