9.4.3. Efficacy Analyses

For lists of objectives and endpoints, refer to Section 3.

Since the superiority of ADP101 at different doses over placebo will be tested, the primary and secondary efficacy analyses will be based on the ITT Population. The primary, secondary, and exploratory efficacy analyses will be performed on the ITT Population, as well as the PP Population (based on the ITT principle). Sensitivity analyses, to be described in full in the SAP, will be performed on subsets of the PP Population, e.g., including or excluding subjects who discontinue study drug prematurely due to treatment-related or unrelated reasons. For efficacy analyses, subjects will be analyzed according to randomized treatment.

Primary and secondary efficacy endpoints will be analyzed using Simes' Test with the Holms procedure (multiple p values will be elaborated in the SAP) and Fisher's exact test for dose selection. All individuals failing to achieve the success in the endpoint definition described above in Section 3 will be considered treatment failures. All individuals who drop out of the study or discontinue study drug prior to undergoing the Exit DBPCFC will be considered treatment failures (i.e., Missing = Failure).

Exploratory efficacy endpoints will be analyzed using descriptive statistics. Details will be included in SAP for the study.

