7.8.1. Primary Efficacy Endpoint and Analysis

The primary endpoint is a ≥ 600 mg desensitization response as determined by tolerating ≥ 600 mg of food protein at the Exit DBPCFC without dose-limiting symptoms for at least 1 qualifying food.

Any subject who does not meet this definition will be considered a non-responder.

Classification as a 1000 mg responder is defined similarly.

Primary Analysis

The primary analysis of the primary endpoint will be performed on pediatric subjects in the ITT Population by treatment group.

The number and percent of subjects with a ≥ 600 mg desensitization response will be reported by treatment group. The primary endpoint hypothesis of superiority of ADP101 over pooled placebo will be tested using the Fisher's exact test. The unadjusted p-values will be reported. The difference in the proportions of responders (ADP101 vs. pooled placebo) with Newcombe 95% CIs will be reported using PROC FREQ procedure in SAS® and the RISKDIFF option.

A sample SAS code for the proc freq is provided below:

Ods output PdiffCL=pdiff

Proc freq

```
data=indata;  
TABLE trtgrp*endpoint/ chisq riskdiff(cl=( newcombe ) correct );  
OUTPUT out=outdata CHISQ RDIF1 ;
```

RUN;

In order to handle the comparison of multiple active groups versus pooled placebo, the overall type-I error will be controlled by the use of the Simes global test (Simes, 1986) with the Holm procedure (Holm, 1979) to adjust for and test the global (joint) hypothesis that at least one of the 2 hypotheses below is rejected.

- H_{01} : proportion of responders in pooled placebo group = proportion of responders in low-dose (1500 mg) group
- H_{02} : proportion of responders in pooled placebo group = proportion of responders in high-dose (4500 mg) group.

The adjustment for multiplicity for the joint hypothesis in support of the primary efficacy endpoint will be performed using the PROC MULTTEST procedure in SAS® (HOLM option). The adjusted p-values will be reported along with the unadjusted p-values described above.

All efficacy-related data will be listed. Tables for the primary efficacy endpoint will include proportion of responders who tolerated at least 600 mg in pooled placebo vs low dose group and pooled placebo vs high dose group in ITT. The unadjusted and adjusted p-values will be displayed.

Sensitivity Analysis

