To assess the robustness of the results in the primary analysis of the primary endpoint using the ITT Population, the following sensitivity analyses will be performed:

1. The primary endpoint will be analyzed for pediatric subjects in the ITT Population using logistic regression model including other factors such as age (years), gender, race, number of food allergies, eliciting dose (median eliciting dose for multiple qualifying foods) at baseline, etc.
2. The same analysis as described in the primary analysis above will be performed using the PP Population.

3. The same analysis as described in the primary analysis above will be performed on the subset of the PP Population that will exclude subjects who discontinue study drug prematurely due to treatment-related or unrelated reasons depending on their exit food challenge status.
4. The same analysis as described in the primary analysis above will be performed on the ITT Population excluding subjects who withdrew from the study prior to completing the Exit DBPCFC for reasons related to COVID-19 (e.g., study site closure).

If 2 or more subjects have missing data, the following sensitivity analyses may be performed:

1. The primary efficacy endpoint will be analyzed using a worst case approach to missing data imputation. Placebo subjects who have missing data (i.e., do not have an Exit DBPCFC) for the primary efficacy endpoint for any reason will be considered responders while ADP101 subjects will be considered non-responders if they have missing data for the endpoint. Analysis methods will follow those described above.
2. If the primary analysis of the primary endpoint shows a statistically significant treatment effect, a tipping point analysis will be conducted to identify the point at which the treatment effect becomes non-significant based on increasing the number of placebo subjects with missing data who are considered responders. The first step will be to test the treatment effect when all ADP101 subjects with missing data are considered non-responders and only one placebo subject with missing data is considered a responder while the remaining placebo subjects with missing data are considered non-responders. If that test shows a statistically significant treatment effect the number of placebo subjects who have missing data that are considered responders will be increased by one until the treatment effect becomes non-significant.

Supportive Analyses

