7.8.3.2. Maximum Tolerated Dose (MTD)

Qualifying Food Allergies (FAs)

For the MTD in qualifying FAs, the following imputation will apply to the endpoints:

- Subjects who do not undergo the Exit DBPCFC have the MTD for the Exit DBPCFC imputed as the MTD at the Screening DBPCFC for the subjects' individual qualifying FAs.
- In order to calculate fold increase of the MTD at the Exit DBPCFC relative to the Screening DBPCFC, if subjects do not tolerate any dose level they will be assigned an MTD of 1 mg.

The following categorical endpoints will be summarized by frequency and percentages of subjects achieving the endpoint for each treatment group.

- Each level of MTD achieved for each qualifying FA at Screening and Exit DBPCFC
- Each level of the relative (fold) increase in MTD from Screening DBPCFC to Exit DBPCFC for each qualifying FA

- Number and percent of subjects with the Exit DBPCFC MTD greater than the Screening DBPCFC MTD for each ADP101 food source based on subjects with corresponding qualifying food allergies
- Number and percent of subjects with the Exit DBPCFC MTD greater than the Screening DBPCFC MTD for at least one food in each ADP101 food/food group (peanut, tree nut, milk, soy, wheat, sesame, finfish, shrimp, and egg) based on subjects with corresponding qualifying food allergies.

The following endpoints will be provided descriptively (median, first and third quartiles [Q1:Q3], min and max) by treatment group.

- Actual value and fold change of MTD between the screening DBPCFC and the Exit DBPCFC of each individual qualifying FA
- Actual value and fold change of the eliciting dose between the screening DBPCFC and the Exit DBPCFC of each individual qualifying FA

Box plot will be provided for MTDs and eliciting doses at the Screening and Exit DBPCFCs across qualifying FAs.

Non-Qualifying Reactive Food Allergies

For non-qualifying reactive FAs, if both screening and exit DBPCFC results are present, the fold increase in MTD from Screening DBPCFC to Exit DBPCFC for that non-qualifying reactive food will be summarized using both continuous and categorical descriptive statistics as described above for qualifying reactive foods.

Similar summary will be provided for eliciting dose.

Box plot will be provided for MTDs and eliciting doses at the Screening and Exit DBPCFCs across non-qualifying reactive FAs.

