7.8.3.3. Neo-Sensitization

Neo-sensitization is defined as subjects who develop confirmed new FAs to previously Non-reactive Foods at Screening, as demonstrated by the Exit DBPCFC.

To determine which subjects would have Exit DBPCFCs on FAs non-reactive at screening, see [Figure 4](#).

The number and percentages of subjects who meet neo-sensitization criteria at any dose level will be summarized by treatment group. As appropriate, the proportions of subjects with neo-sensitization in each ADP101 group versus the pooled placebo group will be compared using the Fisher's exact test. The p-values will be provided. For each food source, the number and percentages of subjects with neo-sensitization at each dose level may be provided as well. The plot of subjects with neo-sensitization at any dose level for any food will be provided.

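### An Early Termination food challenge is permitted, but the SAP's worst-case, tipping-point and new-allergy rules recognise only the Exit challenge, so an observed early result can be recoded or left out

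*Protocol*

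**What the plan says.** The food-challenge row of the protocol's Schedule of Activities (Table 2) marks Screening, Week 40 and ET, each with its own footnote: "Exit DBPCFC: refer to Figure 4. ^ET DBPCFC: consult Study Medical Monitor". SAP Appendix 1 repeats this. On withdrawal, protocol 7.3 states: "If the subject is simultaneously discontinuing study drug and withdrawing early from the study, the ET visit should be conducted". So some early leavers may have an observed challenge result.

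The efficacy rules refer only to the Exit challenge:

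- **Primary.** Protocol 9.4.3: "All individuals who drop out of the study or discontinue study drug prior to undergoing the Exit DBPCFC will be considered treatment failures". SAP 7.8.1 defines response at the Exit challenge and adds: "Any subject who does not meet this definition will be considered a non-responder".
- **Worst case and tipping point (SAP 7.8.1).** The worst-case rule reads "Placebo subjects who have missing data (i.e., do not have an Exit DBPCFC) for the primary efficacy endpoint", for whatever reason, and codes these subjects as responders. ADP101 subjects with missing data are coded non-responders. The tipping-point analysis turns missing placebo subjects into responders one at a time. Both are optional and are considered only if at least 2 subjects have missing data.
- **MTD (SAP 7.8.3.2), Qualifying Foods.** "Subjects who do not undergo the Exit DBPCFC have the MTD for the Exit DBPCFC imputed as the MTD at the Screening DBPCFC".
- **New allergies (SAP 7.8.3.3).** These are "subjects who develop confirmed new FAs to previously Non-reactive Foods at Screening, as demonstrated by the Exit DBPCFC".

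Elsewhere the SAP names the ET visit when it intends to use ET data, for example for the skin-prick test (7.8.3.5), the questionnaires (7.8.3.7) and spirometry (7.9.4).

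**The concern.** A worst-case analysis should bound outcomes that are unknown. Under the written rule it can also reverse one that is known: a placebo child who failed 600 mg at ET has no Exit challenge, so is coded a responder. The same child is available to be flipped in the tipping-point analysis. With about 20 children per comparison group, a few such recodings can decide what the worst case shows.

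Separately, protocol 4.2 presents detection of new allergy to Non-reactive Foods as an important goal of the study. A new allergy confirmed by challenge at ET would not enter the count that addresses it, because the definition requires the Exit challenge.

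**Working it through.** **The plan's own figures.** SAP 3.2 states about 90% power with 16 low-dose, 16 high-dose and 16 placebo completers, and 60 children randomized. Exact enumeration with two-sided Fisher tests and pooled placebo gives 90.9% (Simes) and 90.0% (Holm). The sample size is 48 / (1 − 0.20) = 60. Both reproduce, and ET handling enters neither.

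**Inputs for the illustration.**

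- 20 children per active dose and 10 + 10 = 20 pooled placebo (SAP Table 1 and 6.6).
- Dropout 20% (SAP 3.2): 0.20 × 20 = 4 per group, leaving 16 completers.
- Completers' responders at the planning rates in SAP 3.2: high dose 16 × 0.58 = 9.28, taken as 9; low dose 16 × 0.40 = 6.4, taken as 6; placebo 16 × 0.04 = 0.64, taken as 1.
- Two-sided alpha 0.05 (SAP 6.1) with Holm over two doses (SAP 7.8.1), so the smaller p must be at most 0.025. Its adjusted value is 2 × p.
- m = number of the 4 placebo dropouts with an observed ET failure. The documents give no figure, so the full range 0 to 4 is shown.

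**Worst case.** Placebo responders = 1 + (4 − m); ADP101 dropouts stay non-responders. The row m = 0 is the rule as written, whatever was seen at ET.

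| m kept as failures | Placebo | High 9/20, p | Low 6/20, p | High, Holm-adjusted | Chance of rejecting at least one dose |
|---|---|---|---|---|---|
| 0 | 5/20 | 0.320 | 1.00 | 0.641 | 8.8% |
| 1 | 4/20 | 0.176 | 0.716 | 0.352 | 20.5% |
| 2 | 3/20 | 0.082 | 0.451 | 0.165 | 38.2% |
| 3 | 2/20 | 0.031 | 0.235 | 0.062 | 67.4% |
| 4 | 1/20 | 0.0084 | 0.091 | 0.017 | 88.7% |

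The last column averages over binomial outcomes in 16 completers per group at the planning rates, rejecting if the smaller p is at most 0.025 or both are at most 0.05. At the expected counts, only m = 4 meets Holm's threshold.

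**Tipping point.** Start from 9/20 against 1/20 (p = 0.0084). One flipped placebo subject gives 2/20 (p = 0.031, Holm 2 × 0.031 = 0.062); two give 3/20 (p = 0.082). Adjusted significance is lost at the first flip, whichever subject is flipped. What m changes is how many flips are available, 4 − m. With m = 4 there are none.

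**ADP101 passes at ET.** If these were counted as responders against placebo 1/20, the low dose would move from 6/20 (p = 0.091) to 7/20 (p = 0.044) or 8/20 (p = 0.020). A worst case that counted them could be kinder to ADP101 than the primary analysis, which does not.

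**New allergies.** No arithmetic applies. Where SAP 3.1 describes reassessment of Non-reactive Foods, it says that only a positive challenge defines a new allergy. SAP 7.8.3.3 narrows this to the Exit challenge. An ET challenge that met the first statement would fail the second.

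**The case against.** The strongest reply is that recoding is inferred from silence. The SAP never says that an ET challenge is not an Exit challenge. Protocol Table 9 gives dose schedules for Screening and Exit only, so an ET challenge could be the Exit challenge brought forward. Against this, both schedules footnote the two separately, the Exit evaluation is tied to Week 40, and the SAP names ET for other assessments. If ET was meant to count as Exit, the SAP has to say so, because that reading would also reach the primary endpoint.

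Other parts of the reply stand:

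- The ET challenge is not routine ("ET DBPCFC: consult Study Medical Monitor"), so the number may be small or zero. Subjects who only stop study drug can remain in the study and may have the Exit challenge (protocol 7.2), which narrows the group further.
- The worst-case and tipping-point analyses are optional, and the worst case is a deliberate extreme against ADP101.
- The tipping-point sequence does not depend on which subject is flipped, so a reader told of the ET failures could judge its plausibility.
- No readable text says that an ET challenge would cover a Non-reactive Food. The stated triggers are symptoms or a Week 38 skin-prick change (protocol 8.1.1.1).
- An ET threshold measured at some earlier time is not the 40-week Exit threshold. Keeping the Screening value for MTD is a defensible conservative choice in an exploratory, descriptive analysis.

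**Conclusion.** The point holds for two rules: the definition of missing in the worst-case and tipping-point analyses, and the restriction of new allergies to the Exit challenge. Under the assumptions above, keeping 0 to 4 observed placebo ET failures moves the worst-case high-dose p from 0.320 to 0.0084. The real effect depends on an unknown number of ET challenges and could be nil.

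Four stronger readings are not supported.

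- A reader might infer that the primary result is affected. It is not: anyone without an Exit challenge is a failure by prespecified rule, and an ET failure gives the same answer.
- A reader might infer that the rule turns a significant worst case into a non-significant one. With 10/20 high-dose responders and two ET failures kept, p does fall from 0.19 to 0.041. But if that is the smaller p, Holm gives 2 × 0.0407 = 0.081, and 10/16 = 62.5% exceeds the planned 58%. At 9/20 the same change reaches only 0.082 unadjusted.
- A reader might infer that an ET-confirmed allergy vanishes from the harm data. Reactions at challenge still fall under the food-challenge adverse event category and the listings in SAP 7.9.1. Only the exploratory neo-sensitization count omits it.
- A reader might infer that the Screening imputation for MTD is an error. It is a debatable choice, not a fault.

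**What to change.** Before database lock and unblinding:

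1. State in SAP 7.8.1 that an ET challenge is not an Exit challenge, and leave the primary rule as it is.
2. In the worst-case and tipping-point analyses, treat as missing only placebo subjects with neither an Exit nor an ET result, and keep observed placebo ET failures as failures. Since one Qualifying Food is enough for response, an ET failure should mean that 600 mg was not tolerated for any Qualifying Food, with all of them challenged. A placebo subject who passed at ET stays a responder in the worst case.
3. Keep ADP101 subjects without an Exit challenge as non-responders even if they passed at ET, so that the worst case is never more favourable than the primary analysis.
4. In 7.8.3.3, count a positive ET challenge to a previously Non-reactive Food as a new allergy, flagged as ET-based.
5. In 7.8.3.2, keep the Screening-value imputation and list any ET MTD, with at most a supplementary summary.

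The cost is a few sentences and one derivation flag, with no new data. The downside is that ET results come at varying times before Week 40, which is why they should be flagged. Whether or when an ET challenge should be done is a clinical matter and is not addressed here.

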2. INTRODUCTION

ADP101 is an oral formulation mixture of 15 individual food sources containing allergenic proteins (i.e., almond, cashew, chicken's egg, codfish, cow's milk, hazelnut, peanut, pecan, pistachio, salmon, sesame seed, shrimp, soy, walnut, and wheat; refer to the Investigator's Brochure [IB] for details on each ingredient within ADP101) that are responsible for approximately 90% of food allergies (FAs) in the United States (Boyce, 2010; FDA, 2017; Gupta, 2019). ADP101 is being developed as an oral immunotherapy (OIT) for the treatment of FA triggered by 1 or more of the food sources found in ADP101 in children and adults.

2.1. Study Rationale and Hypothesis

The goal of OIT for FA is to induce a state of clinically meaningful desensitization to food proteins, defined as the absence of moderate or severe allergic reaction following ingestion of small, but potentially dangerous, amounts of food protein. For example, in peanut-allergic subjects, increasing the baseline threshold before immunotherapy from 100 mg or less of peanut protein to 300 mg or more of peanut protein post-immunotherapy reduces the risk of experiencing an allergic reaction by more than 95% for 4 common food product categories that may contain trace levels of peanut residue. This level of risk reduction is highly clinically relevant. Further increase in the threshold to 1000 mg has an additional quantitative benefit in risk reduction (Baumert, 2018; Chinthrajah, 2019).

The existing clinical data from the published literature on single OIT for FAs (Staden, 2007; Varshney, 2011; Burks, 2012; Anagnostou, 2014; Caminiti, 2015; Escudero, 2015; Tang, 2015; Feuille, 2016; Bird, 2018; Elizur, 2019) and of multiple-allergen oral immunotherapy (mOIT) (Begin, 2014a; Begin, 2014b; Andorf, 2018; Andorf, 2019; Chinthrajah, 2019) form the basis for supporting further development of ADP101 as an OIT for the mitigation of allergic reactions, including anaphylaxis, that may occur following accidental exposure to almond, cashew, chicken's egg, codfish, cow's milk, hazelnut, peanut, pecan, pistachio, salmon, sesame seed, shrimp, soy, walnut, and wheat in children and adults aged ≥ 4 to ≤ 55 years.

